**MELVIN AND BREN SIMON
CANCER CENTER**

INDIANA UNIVERSITY

**INTRAOPERATIVE FOLATE TARGETED FLUORESCENCE
IN RENAL CELL CARCINOMA**

INDIANA UNIVERSITY PROTOCOL IUSCC-0546

Title: Intraoperative folate targeted fluorescence in renal cell carcinoma

Test Drug: OTL38: folate conjugated with a Tetrasodium salt solution (C₆₁H₆₃N₉Na₄O₁₇S₄, molecular weight 1414.42) (6 mg/vial) containing 2 mg/mL OTL38 free acid in 3 mL Water for Injection provided by On Target, LLC.

Sponsor/PI: [name]
Professor of Urology, Director of Residency Program and Minimally Invasive Surgery, Department of Urology
Indiana University
[name]
[name]
[contact]
[contact]
[contact]

Co-investigators: [name]
[name], DVM, PhD

Support: On Target Laboratories, LLC

IND#: 127848

Date of Protocol: May 22, 2017

CONFIDENTIALITY

The information contained within this report is confidential and may not be used, divulged, published, or otherwise disclosed without the prior written consent of On Target Laboratories, LLC.

INVESTIGATOR'S AGREEMENT

By signing below I confirm that I have read this protocol and agree:

- To assume responsibility for the proper conduct of this study at this site
- To conduct the study according to the procedures described in this protocol and any future amendments
- Not to implement any deviation from, or changes to, the protocol without written approval from the Institutional Review Board (IRB), except where necessary to eliminate immediate hazard to the subject(s)
- That I am aware of all updates and will comply with all applicable regulations and guidelines

Principal investigator's signature

Date

[name]

Principal investigator's name (print)

Professor of Urology, Director of Residency Program and
Minimally Invasive Surgery, Department of Urology

Principal investigator's title (print)

PROTOCOL SYNOPSIS

Primary Objectives:	To explore the use of OTL38 and fluorescence imaging to visualize renal cell carcinoma (RCC) at the margins of resection in partial nephrectomy and in lymph node(s) or other metastases for radical nephrectomy.
Secondary Objectives:	
To assess the specificity of tumor fluorescence obtained using OTL38 with folate receptor alpha positive (FRα+) renal cell carcinoma cancer lesions detected via immunohistochemistry
 
To assess the agreement between fluorescence imaging using OTL38 and FRα by immunohistochemistry
 
To assess the agreement between fluorescence imaging using OTL38 and visual/tactile assessments
 
To assess inter-observer variation of tumor fluorescence images captured during surgery, physician rated usefulness of imaging, and safety of OTL38

Study Design:	
This is a pilot, phase 2, non-randomized study in patients with RCC, scheduled to undergo primary, partial, or radical nephrectomy. The current study will have 2 separate arms, but the data from each arm will not be compared with each other.
 
Arm 1: patients with partial nephrectomy for localized RCC
 
Arm 2: patients with radical nephrectomy and lymph node dissection for locally advanced or metastatic RCC

Test Drug/Dose:	OTL38 Injection: folate analog ligand conjugated with an indole cyanine-like green dye as a solution in vials containing 3 mL at 2 mg/mL provided by On Target, LLC. Single-dose 0.025 mg/kg administered IV, less than 2 hours prior to skin incision. Diphenhydramine 25 mg will be given prior to administering the study agent.
Duration of Treatment	
Patients will receive a single dose of OTL38 approximately 2 hours before skin incision.
 
Safety assessments will occur at follow-up phone visit at 10 days (± 3 days) and follow-up office visit at 1 month (± 14 days)

Camera Systems	
The da Vinci[®] Fluorescence Imaging Vision System manufactured by Intuitive Surgical, Inc. or the VSiii 3DHD system manufactured by Visionsense will be used in this study to visualize OTL38-labelled tumors during robotic partial and radical nephrectomies. The SPY Elite Imaging System manufactured by NOVADAQ will be used in open radical nephrectomies. These systems are not approved for use with OTL38, and are therefore considered investigational for purposes of this study.
 
The da Vinci[®] Fluorescence Imaging Vision System has integrated fluorescence imaging capable of providing real-time, imaging identification of fluorescently tagged objects.

	
The Visionsense VSiii system is a complete solution enabling surgeons to use a minimally invasive stereoscopic (3D) camera, for Neurosurgical, ENT, Arthroscopy (CE only), and Laparoscopy applications. The system has been successfully used by surgeons in a wide range of MIS procedures. The VSiii system has 510(k) clearance and is CE Mark approved.
 
The SPY Elite Intraoperative Imaging System is a fluorescence imaging system that allows surgeons to capture, review, print and archive high-quality fluorescence images of near infrared (NIR) emitting imaging agents during surgical procedures. The positioning of the Imaging Head is controlled by the surgeon or physician. Image sequence capture is accomplished at operator's command, and images can be replayed immediately for review. When used in combination with indocyanine green, SPY Elite has indications for use that include
 
 • visual assessment of blood flow as an adjunctive method for the evaluation of tissue perfusion, and related tissue-transfer circulation in tissue and free flaps used in plastic, micro-, and reconstructive procedures • visual assessment of blood flow in vessels and related tissue perfusion during gastrointestinal surgical procedures • visual assessment of blood flow in vessels and related tissue perfusion during cardiovascular surgical procedures 
In all other surgical imaging applications – such as for use with targeted NIR imaging agent technologies – SPY Elite is designated as an investigational device.

Enrollment	Subject accrual will take up to 24 months.
Number of Subjects:	
20 patients with RCC will be enrolled in this study.
 
The study will consist of two arms studied simultaneously:
 
 • Arms 1: 10 patients with partial nephrectomy for localized RCC • Arms 2: 10 patients with radical nephrectomy and lymph node dissection for locally advanced or metastatic RCC
Number of Sites	Single site: Indiana University Simon Cancer Center, Indiana University Hospital

Outcomes:	
Partial nephrectomy
 
PRIMARY
 
 Assess the presence and extent of fluorescence of cT1 RCC during partial nephrectomy 
SECONDARY
 
 Pathologic agreement of fluorescence and FR α by immunohistochemistry Agreement between visual and fluorescent images Inter-observer agreement of laparoscopic fluorescent images (for blinded surgeons) Surgeon opinion of usefulness of intra-operative fluorescence imaging-Likert scale questionnaire (Appendix A) Safety (perioperative, 10 days, 1-month)- Vital signs, hematology, chemistry, and adverse events (NCI-CTCAE v4.0)
	
Radical nephrectomy and lymph node dissection
 
PRIMARY
 
 Assess the presence and extent of fluorescence in regional lymph nodes or metastasis in patients with RCC 
SECONDARY
 
 Pattern of nodal spread Agreement of nodal and primary tumor fluorescence Pathologic agreement of fluorescence and FR α by immunohistochemistry Detection of RCC in primary tumor in situ Agreement between visual and fluorescent images. Inter-observer agreement of in-situ fluorescent images (for blinded surgeons) Surgeon opinion of usefulness of intra-operative fluorescence imaging- Likert scale questionnaire (Appendix A) Safety (perioperative, 10 days, 1-month)-Vital signs, hematology, chemistry, and adverse events (NCI-CTCAE v4.0)

LIST OF ABBREVIATIONS AND TERMS

[figure not shown]
Abbreviation/Term	Definition
ADE	Adverse device effect
AE	Adverse event
BMP	Basic metabolic panel
CBC	Complete blood count
CMP	Comprehensive metabolic panel
CRF	Case report form
CT	Computed tomography
CTMS	Clinical Trial Management System
CTO	Clinical Trials Office
CTSI	Indiana Clinical and Translational Sciences Institute
DSMC	Data Safety Monitoring System
ECOG	Eastern Cooperative Oncology Group
FDA	Federal Drug Administration
FR	Folate receptor protein
FITC	Fluorescein isothiocyanate
GFR	Glomerular filtration rate
IDS	Investigational Drug Service
IHC	Immunohistochemistry
IND	Investigational new drug
IUH	Indiana University Hospital
IUSCC	Indiana University Simon Cancer Center
LND	Lymph node dissection
REDCap	Research Electronic Data Capture
RCC	Renal cell carcinoma
SAE	Serious adverse event
SEER	Surveillance epidemiology and end results

2 SCHEMA

3 BACKGROUND

Renal cell carcinoma (RCC) has the highest early mortality or potential years of life lost of all urologic malignancies and this trend is increasing according to the recent SEER database analysis from 1973 to 2006 (Kamel 2012). Computerized tomography (CT) imaging are used more often for detecting renal masses and has led to distinct groups of RCCs: localized (stage I-II) with a high cure rate and advanced (stage III-IV) with high rates of distant metastasis and early mortality. Partial nephrectomy and radical nephrectomy are standard treatments for renal

masses. Although these options demonstrate better survival, there are uncertainties related to the comparative effectiveness of these treatment options (Tan 2012). Nonetheless, surgery remains an integral part of the treatment strategy for all stages of RCC, and the ability to accurately image the disease in real time is becoming increasingly important for both localized and advanced disease.

3.1 Localized RCC

Localized RCC is a cancer of the kidney that has not spread to the lymph nodes or distant organs. Improved sensitivity of CT imaging procedure has led to the increased incidence of incidentally diagnosed, small, low stage RCC lesions than based on the classic triad of symptoms (hematuria, palpable mass, and pain) that occurs in less than 15% of RCC cases (Palapattu 2002). According to a study using the data from the National Cancer Database, a greater proportion of newly diagnosed patients with RCC present with localized RCC (lower stages) than in earlier years. The number of patients with Stage 1 localized RCC increased from 55% in 1993 to 67% in 2004 (Kane 2008).

Sparing renal parenchyma in addition to cancer control has traditionally been viewed as an important and an unmodifiable variable in surgical treatment, especially in organ-sparing surgery or partial nephrectomy of localized RCC. Although healthy parenchymal safety margin during conservative renal surgery is still the standard of care, the risks of significant complications increase with the technical complexity of the case.

Limiting ischemia time has been used as an important modifiable factor during partial nephrectomy. Recent studies show that preoperative glomerular filtration rate (GFR) and percentage of parenchyma spared are the best predictors of long term GFR (Lane 2011; Simmons 2011). At the same time, the size of the safety margin during partial nephrectomy has not been effective in predicting recurrence (Berdjic 2006). Tumor enucleation for RCC (resecting along the pseudocapsule of the tumor instead of obtaining a safety margin) has been tried to spare renal parenchyma, limit blood loss, and resect anatomically challenging tumors. Contrasting results have been reported in studies relating the effectiveness of enucleation versus partial nephrectomy (Minervini 2009; Minervini 2011). Acceptance of enucleation has been slow due to the rate of pseudocapsule invasion and concern over incomplete tumor removal.

3.2 Advanced RCC

Between 1990 and 2006 the death rate decreased 21% on average for all malignancies in the US, but for kidney cancer it decreased by 6.9% (Jemal 2010). This placed kidney cancer 11th out of the 16 reported malignancies in the SEER database in terms of improving death rate. Despite the introduction of several new systemic therapies for advanced RCC, there are limited options that offer a reliable complete response. Cytoreductive nephrectomy continues to be the standard of

care, but the role for lymph node dissection is under investigation. We propose investigating the ability of real-time targeted imaging with folate tagged fluorescence to determine who should undergo lymph node dissection (LND) and the extent of that dissection.

Of those undergoing nephrectomy for localized disease, up to 18% will have recurrence or progression (Crispen 2008). Theoretically, many of these could benefit from a LND. However, as partial nephrectomy replaces radical nephrectomy for larger tumors, arguably fewer LNDs will be performed. Although previous studies have concluded that a LND can provide a durable progression free survival, the criteria for selection of patients who will most likely benefit from a LND remains a challenge (Delacroix 2011).

Templates for LNDs continue to vary based on surgeon preferences, however, a recent study examined the predictability of 5 previously identified high-risk pathologic features on lymph node metastases prior to developing surgical template for LNDs (Crispen 2008). Patients with 2 or more of the 5 criteria previously identified by Blute et al (Blute 2004) — nuclear grade 3 or 4, presence of a sarcomatoid component, tumor size ≥ 10 cm, tumor stage pT3 or pT4, and histological tumor necrosis— were considered high-risk for nodal metastases. A total of 64/169 (38%) patients had positive lymph nodes. The lymph node positivity rate was directly proportional with the number of criteria identified: 20%, 39%, 49%, and 50% for 2, 3, 4, and 5 criteria present, respectively. Lymph node spread was assessed by examining 5 different landing zones (right hilar, pre-caval, inter-aortocaval, pre-aortic, and left hilar). For right-sided tumors, 45% of positive cases had a lack of hilar region involvement. So, if only the hilar nodes (those closest to the kidney) were sampled, then 45% of positive node cases on the right would have been missed. The hilar nodes are the easiest to remove surgically during an LND and are often the only nodes removed. Intraoperative imaging of tumors can enable surgeons to visualize and perform LNDs that could result in improved clinical outcomes.

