Surrounding perinephric fat will be removed as indicated for the renal mass. Then the renal mass will be visualized and photographed (video and still images) using visible light and fluorescent light. As described above, start and stop times of exposure to fluorescent light will be noted, and the number and location of fluorescent lesions related to the mass and surrounding renal parenchyma detected will be recorded on the schematic. Findings under visible light will also be recorded.

After the renal mass is removed, it will be processed by the operating surgeon and the frozen section pathology staff. The tumor margin will be inked and the tumor sectioned in 5mm thick cross-sectional slices. The tumor will then be returned to the operating room to be viewed and photographed with visible and fluorescent light. It will then be sent for pathologic processing as discussed in **Appendix B**.

For Radical Nephrectomies

The regional lymphadenectomy will be performed as per the standard of care for the patient’s renal mass. The renal mass will be visualized and photographed (video and still images) using visible and fluorescent light *through the surrounding perinephric fat*. The start and stop times of exposure to fluorescent light will be noted, and the number and location of fluorescent lesion/s related to the mass and surrounding renal parenchyma detected under fluorescent and visible light sources will be recorded on the schematic.

All identified nodal tissue from each marking (“O”, “X”, and “⊗”) will be excised, as determined by the Investigator, *under normal light*. Following the initial excision under normal light, the field will be illuminated with *fluorescent light* again to detect any remaining fluorescence-positive lesions. Any such lesions will be noted with a “P” on a schematic sheet (**Appendix C**) and excised as determined by the Investigator. A unique identifier will be assigned to each excised lesion, and the location for each lesion will be recorded on the schematic and in the eCRF. The reason for not excising any remaining lesion(s) will be noted. If no additional lesions are observed, this will be noted on the schematic and in the eCRF.

The nodal tissue will be processed by the operating surgeon and the frozen section pathology staff. The lymph nodal tissue will be marked with suture or clips to help with anatomic orientation of the specimen, and then sent for pathologic processing as discussed in the study pathology manual.

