12.7 Analysis of primary objective

The primary endpoint is to see if OTL38 and fluorescence imaging has sensitivity to detect RCC in the primary tumor (for partial nephrectomy) or in lymph nodes (for radical nephrectomy with lymph node dissection). Both sensitivity and the secondary endpoint of specificity will be assessed as follows: Final pathology and immunohistochemistry will serve as the gold standard with which gross observation and fluorescent imaging are compared for margin of resection, regional lymph nodes, and primary tumor. Pathology and immunohistochemistry results will be listed per patient. Times on and off for the imaging system will be listed per patient. Sensitivity, specificity, positive predictive value, and negative predictive value will be calculated for descriptive purposes although we understand the sample sizes are not large enough to estimate these values with a high level of accuracy at this stage. That would be accomplished in a future larger study. Sensitivity and specificity will be estimated using the method of Generalized Estimating Equations (GEE), which will take into consideration the correlated nature of multiple lesions removed from the same patient. Each patient will have all excised target lesions contributing to the data analysis (each type: O, x, ⊗, and P).

	Cancer +	Cancer-
Fluorescence+	True Positive (TP)	False Positive (FP)
Fluorescence-	False Negative (FN)	True Negative (TN)

Sensitivity (proportion of true positives) = $(TP/TP+FN) \times 100$

Specificity (proportion of true negatives) = $(TN/FP+TN) \times 100$

Sensitivity will be estimated using the GEE model for binomial distribution with fluorescence (-, +) as the fixed effect and patients as a random effect, and the 95% lower one-sided confidence interval for the true sensitivity will also be estimated. Specificity will be estimated using the GEE model for binomial distribution with fluorescence (-, +) as the fix effect and patients as a random effect, and the 95% lower one-sided confidence interval for the true specificity will also be estimated. Positive and negative predictive value will be estimated using similar methods.

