12.8 Analysis of secondary objectives

Specificity: The analysis for specificity is described above.

Detection of RCC in primary tumor (radical nephrectomy arm only): This analyses will be the same as for the primary objective in the partial nephrectomy arm. Pattern of nodal spread will be described qualitatively.

Agreement between pathological agreement between fluorescence and FR α by IHC: This endpoint will also be assessed by Kappa statistics (for presence/absence) or Intra Class Correlation (for numerical measures). Agreement between nodal and primary tumor fluorescence in the radical nephrectomy arm will be assessed similarly.

Agreement between visual and fluorescent images: Kappa statistics will be used to assess agreement between visual and fluorescent images. In addition, the number of lesions detected by

usual visible/tactile conditions and/or palpation vs fluorescent imaging will be analyzed using a paired t-test.

Inter-observer agreement: Kappa statistics will be used to assess inter-observer agreement between of captured fluorescent images.

Usefulness: Responses to the Likert scale questionnaire completed by the surgeons will be listed and summarized

Safety: Vital signs will be summarized using descriptive statistics. Clinical chemistry, hematology, and urinalysis laboratory values will be listed in tabular format and those with above or below normal range will be identified within the table. AEs and TEAEs will be summarized by body system and presented by severity and causal relationship to study drug. ADEs will be summarized by body system and presented by severity and causal relationship to study device. Patients experiencing serious AEs or serious ADEs will be listed and summarized in tabular format.

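### Arm 2 nodal sensitivity is biased upward wherever a node is removed only because it fluoresces, since a dark cancerous node there can never count as a false negative

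*Combined protocol and SAP*

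**What the plan says.** **The field.** For radical nephrectomy, Section 8.3.2.2 states: "The regional lymphadenectomy will be performed as per the standard of care for the patient’s renal mass". It names no template or list of zones. Section 3.2 says "Templates for LNDs continue to vary based on surgeon preferences" and, of general practice, "The hilar nodes are the easiest to remove surgically during an LND and are often the only nodes removed". Citing a published series that mapped five landing zones, it adds: "For right-sided tumors, 45% of positive cases had a lack of hilar region involvement".

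**What is removed.** Section 8.3.2.2 marks lesions O (visible light or palpation), X (fluorescence only) or ⊗ (both). "All identified nodal tissue from each marking" is to be excised, subject to the investigator's decision. After that excision the field is lit again with fluorescent light. Lesions that still glow are marked P and excised, again at the investigator's decision, and a reason is noted for any lesion left in place.

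**What is analysed.** Section 12.7 uses pathology and immunohistochemistry as the reference and says: "Each patient will have all excised target lesions contributing to the data analysis". It lists the types as O, x, ⊗ and P. Section 12.3 says that an observed sensitivity below 70% in either arm would lead the team to consider refining the method before larger studies.

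**Nodal spread.** Section 12.8 says only: "Pattern of nodal spread will be described qualitatively".

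**The concern.** The reference standard exists only for excised tissue, and for some nodes the test under study influences excision. This is partial verification. A normal-looking cancerous node outside the tissue removed as standard care is counted if it glows and is excised. If it is dark, it stays in the patient and never reaches the two-by-two table. P lesions show this most clearly, because they are what the initial excision left behind and they are found only by fluorescence.

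The GEE model in Section 12.7 deals with correlation among lesions from one patient. It does not deal with selective verification, and no other correction is planned.

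At stake are the Arm 2 primary estimate and the one numerical criterion attached to it. An upward bias weakens the 70% rule in the direction in which it is meant to protect. The nodal-spread description is also affected, because the plan has no rule separating a zone found free of cancer from one that was not dissected. Section 3.2 gives the choice and extent of dissection as a purpose of the imaging.

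**Working it through.** **The plan's own figure.** Section 12.3 gives no expected value or precision for sensitivity. Its one computed figure concerns toxicity: 1 − 0.9^20 = 0.878, which reproduces the stated 88%. It has no bearing on this point.

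**Step 1: which cancerous nodes can be counted (Sections 8.3.2.2 and 12.7).**

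| Cancerous node | Removed? | Role in Section 12.7 |
|---|---|---|
| Removed as standard care, marked O, X or ⊗ | Yes | True positive or false negative |
| Removed as standard care, unmarked (normal-looking and dark) | Yes | No listed type; may drop out as a false negative |
| Not removed as standard care, normal-looking, glows (X or P) | At the investigator's decision | True positive |
| Not removed as standard care, normal-looking, dark | No | Never counted |

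**Step 2: formula.** Let Se be the true sensitivity and q the share of *all* cancerous nodes that are normal-looking and would be removed only if they glow. Assume that every such glowing node is excised, that all other cancerous nodes are verified and counted, and that Se is the same in both groups. Per cancerous node, true positives are Se and verified false negatives are (1 − q)(1 − Se). Then

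observed sensitivity = Se / [Se + (1 − q)(1 − Se)] = Se / [1 − q(1 − Se)].

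The true value that reads as 70% is 0.7(1 − q) / (1 − 0.7q).

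**Step 3: results.** The documents do not give q, so a range is assumed. Its top borrows the 45% in Section 3.2.

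| q | True 50% reads | True 60% reads | True 70% reads | True value that reads 70% |
|---|---|---|---|---|
| 10% | 52.6% | 62.5% | 72.2% | 67.7% |
| 20% | 55.6% | 65.2% | 74.5% | 65.1% |
| 30% | 58.8% | 68.2% | 76.9% | 62.0% |
| 45% | 64.5% | 73.2% | 80.9% | 56.2% |

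Example: at Se = 0.60 and q = 0.20, 0.60 / (1 − 0.20 × 0.40) = 0.60 / 0.92 = 0.652.

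**Step 4: where the threshold is crossed.** A true 60% reads 70% when 0.60 / (1 − 0.40q) = 0.70, that is q = (1 − 0.60/0.70) / 0.40 = 0.357. Of the four rows, only 45% exceeds this.

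**Step 5: discounting the 45%.** That figure says nothing about whether the nodes looked normal. If half did (assumed), q = 22.5% and a true 60% reads 0.60 / 0.91 = 65.9%. If 30% did, q = 13.5% and it reads 0.60 / 0.946 = 63.4%.

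**Step 6: effect on the 70% rule.** With 10 independent verified cancerous nodes (assumed), the chance of at least 7 positive is 0.38 at 60% and 0.73 at 73.2%. The standard error at 60% is √(0.6 × 0.4 / 10) = 0.155, about 15 points.

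**The case against.** The strongest reply is that the documents never say that fluorescence takes excision beyond the standard field. Section 8.3.2.2 speaks of relighting the field, which suggests tissue already exposed, and it leaves excision to the investigator. Appendix D (Section 19.4.1) says that labelling will not decide whether a suspected mass is removed. If fluorescence triggered no excisions, this bias would not arise among the nodes that are removed. This part stands as a limit on size. It does not remove the problem, because Section 8.3.2.2 expressly provides for excising X and P tissue, and P lesions are selected by fluorescence even inside the field. The two sections pull apart and need reconciling.

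Second, 45% is no estimate of q. It is a per-patient figure for right-sided tumours, with no component for normal appearance. Section 6.2 requires CT evidence of nodal or metastatic disease, so many positive nodes may already look suspicious and carry an O. This stands.

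Third, Section 12.7 calls the accuracy figures descriptive, missing 70% leads only to considering refinement, and a bias of 2.5 to 5 points at q = 10% to 20% is small beside a standard error near 15 points. This also stands, and it lowers the urgency. But sampling error goes both ways and shrinks in a larger study, whereas this bias goes one way and would carry over with the design.

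A reader might also infer that undissected zones will be reported as clean. Nothing in the plan codes them negative, and Section 12 says that missing data are not imputed. The Appendix C drawing is not visible in the text reviewed and the pathology manual is not part of it, so any zone recording there cannot be checked. What can be said is that Section 12.8 gives no rule.

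**Conclusion.** The concern holds in a limited form. Wherever removal depends on fluorescence, Arm 2 nodal sensitivity is biased upward for any q above zero and any true sensitivity below 100%, and the 70% rule takes on that bias.

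The size cannot be derived from the documents. Under the stated assumptions a true 60% gains 2.5 points at q = 10%, 5.2 at 20%, 8.2 at 30% and 13.2 at 45%. The 45% row is an illustrative extreme. CT-evident disease and investigator discretion would both lower the effect.

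Two stronger readings are not supported: that fluorescence certainly extends the dissection beyond the standard field, and that an agent with 60% sensitivity should be expected to pass. The second needs q above about 36%, and nothing in the documents establishes that.

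The change is worth making because it is cheap and concerns a primary estimate. It does not call the trial's conduct into question.

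**What to change.** 1. **Record before imaging.** Before the camera is used, note on the surgical schematic which landing zones will be dissected as standard care. The five zones described in Section 3.2 would serve as the list.
2. **Section 12.7, main analysis.** Compute Arm 2 nodal sensitivity, and apply the 70% rule, from all nodes removed in those zones as standard care, *marked or unmarked*. State explicitly that an unmarked cancerous node counts as a false negative.
3. **Section 12.7, separate report.** Report X nodes from other zones, and all P nodes from any zone, as additional cancers found and additional benign nodes removed. P nodes stay out of the main figure because they are removed only on account of fluorescence.
4. **Section 12.8.** In the nodal-spread description, label undissected zones *not assessed*.
5. **Reconcile** the Appendix D statement on labelling and removal with the excision of X and P tissue in Section 8.3.2.2. Which of them should govern is a matter for the investigators.

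The cost is a few tick boxes and some analysis wording, with no extra patients and no change to surgery. The price is a main figure that rests on fewer nodes and may be lower, since some cancers found only by fluorescence leave the numerator.
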